9.5.8 Adjustment for Multiplicity

There will be no adjustment for multiplicity in this study.

9.6 Safety Analyses

All safety analyses will be based on the Safety Population on the locked database after all patients have completed the 12 month follow-up visit or are lost to follow-up.

9.6.1 Adverse Events

Safety summaries will include the incidence of treatment-emergent adverse events (TEAEs). TEAEs are defined as any adverse event (AE) that began on or after the date of treatment or worsened in severity or frequency after treatment was initiated. Events worsening in severity should be considered new AEs.

All TEAEs will be coded using the Medical Dictionary for Regulatory Activities (MedDRA) and summaries will present data by System Organ Class (SOC) and Preferred Term. TEAEs will be graded for severity into 1 of 5 classes following CTCAE version 4.0 criteria.

TEAEs will be summarized both based on the number of patients experiencing an event and as a summary of total number of TEAEs experienced by MedDRA, SOC, and Preferred Term.

A summary table will be created summarizing the number and percentage of patients with the following:

- At least one TEAE
- At least one severe TEAE
- At least one TEAE related to the study procedure or study device
- At least one treatment-emergent SAE
- At least one treatment-emergent SAE related to the study procedure or study device
- At least one TEAE leading to discontinuation of study participation
- At least one TEAE resulting in death

Separate summaries will be generated for the following types of TEAEs:

- Overall TEAEs
- Severe TEAEs
- TEAEs related to the study procedure or study device
- SAEs
- SAEs related to the study procedure or study device
- TEAEs resulting in death

9.6.2 Laboratory Evaluations

All laboratory parameters will be presented in the data listings. All pre-treatment laboratory findings determined to be clinically significant by the Investigator will be reported as concurrent medical conditions. All clinically significant post treatment laboratory results will be reported as adverse events if they have worsened since baseline.

9.6.3 Vital Signs

Vital sign data will be presented in the data listings. All pre-treatment vital signs determined to be clinically significant by the Investigator will be reported as concurrent medical conditions. All clinically significant post treatment vital sign results will be reported as adverse events if they have worsened since baseline.

9.6.4 Physical Examination Results

Data from physical exams will be presented in the data listings. All pre-treatment physical exam findings determined to be clinically significant by the Investigator will be reported as concurrent medical conditions. All clinically significant findings on exams performed after treatment will be reported as adverse events if they have worsened since baseline.

9.6.5 Concomitant Medications

Concomitant medications data will be presented in the data listings.

9.7 24 Month Follow-Up Data

The data described in section 5.4 will be collected at the 24 month follow-up visit.

Data collected during the 24 month follow visit will be summarized separately from the data collected during the initial 12 month post PAE study period. All 24 month follow-up visit data recorded on the CRF will be included in the data listings. Select 24 month follow-up data may summarized, including change from baseline values, where applicable.

10. Records, Confidentiality and Data Monitoring

Each patient will be identified by study ID number only in the trial records. Study data will be recorded on pre-printed CRFs. Monitoring of study data recorded on source documents and reported on study CRFs will be conducted for all patients to ensure accuracy and completeness.

11. Quality Control and Assurance

It will be the responsibility of the Principal Investigator to ensure that data collection and reporting is complete and accurate.

12. Good Clinical Practice

This investigation will be conducted in accordance with the International Conference on Harmonization (ICH) E6 for Good Clinical Practice (GCP): Consolidated Guidance and all appropriate regulatory requirements. The Investigator will be thoroughly familiar with the appropriate use of the treatment procedure as described in the protocol. Essential clinical documents will be maintained to demonstrate the validity of the study and the integrity of the data collected. Master files will be established by the site personnel at the beginning of the study, maintained for the duration of the trial and retained according to all appropriate regulations.

13. Ethical Considerations

The study will be conducted in accordance with ethical principles founded in the Declaration of Helsinki. The Institutional Review Board (IRB) will review all appropriate study documentation, including the protocol, informed consent and any advertisements that will be used for the study, in order to safeguard the rights, safety and well-being of the patients. The study will only be conducted once IRB approval has been obtained. Safety updates, annual progress reports and any revisions to these documents will be provided to the IRB by the Principal Investigator as required by regulations.

14. Patient Information and Informed Consent

Appendix A: Schedule of Events

	Visit -1	Visit 1	Visit 2	Visit 3	Visit 4	Visit 5
	Screening/ Baseline (within 4 weeks of Day 1)	Treatment (Day 1)	Month 1 (4 weeks ± 2 weeks)	Month 6 (24 weeks ±2 weeks)	Month 12 (52 weeks ± 2 weeks)	Month 24 (104 weeks ± 2 weeks)
Informed Consent	X					
Eligibility criteria assessment	X					
Demographics	X					
Transrectal Ultrasound	X		X	X	X	X
Transabdominal Ultrasound	X		X	X	X	X
Medical History	X					
Concurrent Medical Conditions	X					
Physical Examination	X		X	X	X	X
Vital signs	X		X	X	X	X
Blood tests	X		X	X	X	X
Urinalysis	X		X	X	X	X
PSA	X		X	X	X	X
IPSS	X		X	X	X	X
IIEF	X		X	X	X	X
Uroflowmetry	X		X	X	X	
PAE		X				
Cystoscopy			X ¹	X ¹	X ¹	
Proctoscopy			X ¹	X ¹	X ¹	
Adverse Events		X	X	X	X	
Concomitant Medications	X	X	X	X	X	
Protocol violations	X	X	X	X	X	

¹ Cystoscopy and/or anoscopy will be performed for signs or symptoms of bowel or bladder injury, including hematuria, blood per rectum, or greater than expected pelvic pain at any time during the study protocol.

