After treatment with PAE, follow-up visits will take place at 1, 6 12, and 24 months, ± 2 weeks, from the day of treatment. A Schedule of Events and Study Flow Chart are provided in Appendices A and B, respectively. Cystoscopy and/or anoscopy will be performed for signs or symptoms of bowel or bladder injury, including hematuria, blood per rectum, or greater than expected pelvic pain at any time during the study protocol. Certain medical conditions, such as neurogenic bladder, detrusor failure, and urethral stenosis, may mimic LUTS due to BPH. Urodynamic testing will be obtained at baseline for patients with clinical symptoms or history concerning for these conditions.

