5.2 Visit 1: Prostate Artery Embolization (PAE)

The PAE procedure will be performed within 4 weeks of baseline prostate ultrasound. PAE with Embosphere Microspheres will be performed according to the technical procedure provided in Appendix C.

Treatment data recorded will include the following:

- Total fluoroscopy time
- Total radiation dose
- Number and origins of arterial supply
- Volume and size of embolic material delivered
- Evidence of collateral blood supply
- Duration of hospitalization
- Sedative medications administered
- Patient pain score before and after procedure

- Procedure adverse events

5.3 Visits 2, 3, 4: 1 Month, 6 Months, 12 Months (4 weeks, 24, 52 ± 2 weeks post PAE)

Patients will have the following assessments performed:

- Physical exam, including vital signs
- IPSS and IIEF questionnaires
- TRUS of the prostate
- TAUS of the bladder
- Laboratory evaluations, including a complete blood count (CBC), complete metabolic panel (CMP), urinalysis, urine culture, and prostate specific antigen (PSA)
- Uroflowmetry to assess Qmax
- Cystoscopy, if clinically indicated
- Proctoscopy, if clinically indicated
- Review of concomitant medications and adverse events

Patients who are unable or unwilling to return for follow-up will be contacted by telephone, email, or mail to administer the IPSS and IIEF questionnaires, and to report any new treatments for BPH and/or LUTS.

5.4 Visit 5 (Long Term Follow-Up): 24 Months (104 ± 2 weeks post PAE)

Patients will have the following assessments performed:

- Physical exam, including vital signs
- IPSS and IIEF questionnaires
- TRUS of the prostate
- TAUS of the bladder
- Laboratory evaluations, including a complete blood count (CBC), complete metabolic panel (CMP), urinalysis, urine culture, and prostate specific antigen (PSA)
- Uroflowmetry to assess Qmax

Patients who are unable or unwilling to return for follow-up will be contacted by telephone, email, or mail to administer the IPSS and IIEF questionnaires, and to report any new treatments for BPH and/or LUTS.

6. Withdrawal of Patients

Patients will be informed that they have the right to withdraw from the study at any time for any reason, without prejudice to their medical care. The Investigator also has the right to withdraw patient from the study for any of the following reasons:

- Adverse event
- Concurrent medical condition
- Patient unwillingness to comply with study requirements
- Patient death
- Other Investigator decision

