9.5.1 International Prostate Symptom Score (IPSS)

The primary efficacy outcome will be based on the IPSS. The IPSS is a frequent used, validated, 8 item (7 symptom burden questions and 1 quality of life question) instrument which can be serially performed to compare the progression of symptoms and their severity over months and years. Patients are asked to assess how often they have experienced the following 7 symptoms in the past month: incomplete emptying, frequency, intermittency, urgency, weak urine stream, straining and nocturia. The response categories range from 0=Not at all to 5=Almost always. The total IPSS score is calculated by summing the responses for the 7 symptom burden items. The eighth item is an assessment of patient quality of life due to LUTS and does not contribute to the IPSS score calculation.

Patients will be classified into one of 3 symptom severity categories based on their total IPSS score as follows:

- Mildly symptomatic: 0-7
- Moderately symptomatic: 8-19
- Severely symptomatic: 20-35

The IPSS total score will be summarized for the baseline, 1 month, 6 month and 12 month time points, including change from baseline. Change from baseline will be calculated as post baseline IPSS score minus baseline IPSS score. A negative value indicates symptom improvement. 95% confidence intervals will be calculated for the mean change from baseline to the post baseline time points. For informational purposes, IPSS scores will also be summarized separately for patients that receive unilateral and bilateral PAE if there are sufficient numbers in both groups.

The primary efficacy analysis will be the change in IPSS total score from baseline to 12 months post PAE for the ITT population. A Paired-Sample Wilcoxon Signed Rank Test will be used to assess the statistical significance of the change from baseline to 12 months post PAE. A secondary analysis of the proportion of patients who have improved by at least one IPSS symptom category (i.e., severe to moderate, severe to mild, or moderate to mild) from baseline to 12 months post PAE will also be performed. A 95% confidence interval will be calculated for the proportion. The proportion of patients improving at least 3 points on the IPSS total score at the 12 month time point will also be summarized and the corresponding 95% confidence interval will be calculated.

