9.5.7 Handling of Missing and Spurious Efficacy Data

All available data for treated patients will be included in the by-patient data listings and summary tables.

Obvious outliers for continuous data will be investigated and data queries will be generated as appropriate. If an outlier is determined to be a valid response, the summary analyses may be performed both including and excluding the outlier in order to evaluate the impact on the summary statistics. All outliers impacting the summary analyses will be discussed in the study report.

In the ITT analyses for the IPSS, IIEF, PSA and uroflowmetry variables, a Last Observation Carried Forward (LOCF) approach will be used. If a patient does not have any valid post-baseline data for a given outcome, the baseline value will be carried forward. This approach conservatively assumes there has been no improvement for those patients with completely missing post-baseline data. In addition, sensitivity analyses will be performed to determine the robustness of the ITT results using multiple imputation techniques if the data are determined to be missing at random.

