Appendix D: International Prostate Symptom Score (IPSS)

	Not at all	Less than 1 time in 5	Less than half the time	About half the time	More than half the time	Almost always	YOUR SCORE
Incomplete emptying Over the past 4 weeks, how often have you had a sensation of not emptying your bladder completely after you finish urinating?	0	1	2	3	4	5	
Frequency Over the past 4 weeks, how often have you had to urinate again less than two hours after you finished urinating?	0	1	2	3	4	5	
Intermittency Over the past 4 weeks, how often have you found you stopped and started again several times when you urinate?	0	1	2	3	4	5	
Urgency Over the past 4 weeks, how difficult have you found it to postpone urination?	0	1	2	3	4	5	
Weak stream Over the past 4 weeks, how often have you had a weak urinary stream?	0	1	2	3	4	5	
Straining Over the past 4 weeks, how often have you had to push or strain to begin urination?	0	1	2	3	4	5	
	None	1 Time	2 Times	3 Times	4 Times	5 or More Times	
Nocturia Over the past month, many times did you most typically get up to urinate from the time you went to bed until the time you got up in the morning?	0	1	2	3	4	5	
IPSS Total Score	0-7=Mildly symptomatic, 8-19=Moderately symptomatic, 20-35=Severely symptomatic						
	Delighted	Pleased	Mostly Satisfied	Mixed – almost equally satisfied and dissatisfied	Mostly dissatisfied	Unhappy	Terrible
Quality of life due to urinary symptoms: If you were to spend the rest of your life with your urinary condition the way it is now, how would you feel about that?	0	1	2	3	4	5	6

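### Month-1 IPSS and IIEF may be collected from day 14, so up to half of their 4-week recall period can lie before PAE

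*Combined protocol and SAP*

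**What the plan says.** **Timing.** The Appendix A column for visit 2 reads "Month 1 (4 weeks ± 2 weeks", with IPSS and IIEF both marked. The Section 5 text applies the same tolerance to every visit: "follow-up visits will take place at 1, 6 12, and 24 months, ± 2 weeks, from the day of treatment". The Section 5.3 heading prints the tolerance once, after the last of its three visits ("4 weeks, 24, 52 ± 2 weeks post PAE"). Read alone, that could suggest no window at month 1, but Section 5 and Appendix A leave no doubt that it applies.

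**Recall periods.** In Appendix D, six of the seven IPSS symptom items use a 4-week look-back, for example "Over the past 4 weeks, how often have you had a sensation of not emptying your bladder completely" and "Over the past 4 weeks, how often have you had a weak urinary stream". The seventh, nocturia, differs: "Over the past month, many times did you most typically get up to urinate". Section 9.5.1 describes the whole symptom score by the longer period: "how often they have experienced the following 7 symptoms in the past month". All 15 IIEF items in Appendix E use 4 weeks. The IPSS quality-of-life item asks about the present condition and has no look-back.

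**Use of the data.** Sections 9.5.1 and 9.5.5 summarise the month-1 change from baseline in IPSS total and in each IIEF subscale, with 95% confidence intervals. The primary analysis is the 12-month change in IPSS total. For missing IPSS and IIEF values, Section 9.5.7 states that "a Last Observation Carried Forward (LOCF) approach will be used".

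Nothing in the documents tells patients to answer only for the time since PAE, shortens recall at month 1, or sets early visits aside.

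**The concern.** A score collected before day 28 is labelled post-baseline, but part of what the patient is asked to recall is his untreated state. How much depends on the day he attends, so patients at the same nominal visit do not report on the same post-treatment period, and no planned analysis allows for this.

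Two planned outputs are exposed. For the IPSS total, pre-treatment days would tend to shrink the month-1 improvement. For the IIEF, the same pull toward zero is not conservative: Section 7.1 and Appendix C list erectile dysfunction as a risk of PAE, and mixing in pre-PAE function could mask an early decline.

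There is also a narrow route to the 12-month result, because LOCF can carry a month-1 score forward.

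**Working it through.** The documents state no overlap figure to reproduce, so this is direct arithmetic on the visit window and the recall periods.

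**Inputs**
- Month-1 window: 4 weeks ± 2 weeks, that is 28 ± 14 = days 14 to 42, counted as elapsed days since PAE (Section 5, Appendix A).
- Recall R: 28 days for six IPSS symptom items and all IIEF items (Appendices D and E).
- Nocturia: past month, taken as 28 to 31 days (assumption).

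**Formula.** For a visit on day d, the share of recall before PAE is max(0, R − d) / R.

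| Visit day | R = 28 | R = 30 (nocturia) | R = 31 (nocturia) |
|---|---|---|---|
| 14 | 14/28 = 50% | 16/30 = 53% | 17/31 = 55% |
| 21 | 7/28 = 25% | 9/30 = 30% | 10/31 = 32% |
| 28 | 0% | 2/30 = 7% | 3/31 = 10% |
| 35 or later | 0% | 0% | 0% |

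**Average over the window.** Assume visits fall evenly on the 29 days from 14 to 42.
- Early visits (days 14 to 27): 14/29 = 48%.
- Sum of shares over those days: (14 + 13 + … + 1)/28 = 105/28 = 3.75.
- Mean share among early visits: 3.75/14 = 27%.
- Mean share over all visits: 3.75/29 = 12.9%, about 13%.

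**Calendar-month reading of Section 5.** If month 1 is anchored at day 30 or 31, the earliest visit is day 16 or 17. The maximum share for the 4-week items is then 12/28 = 43% or 11/28 = 39%. The overlap is smaller but remains.

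**Other visits.** The earliest 6-month visit is week 22, day 154. The share there and at 12 and 24 months is 0%, so the mismatch is confined to month 1.

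**Illustration in score points, not an estimate.** Section 1 cites an initial 15-patient series with a 6.7-point improvement in severity score, in a sentence reporting 1-month results. Suppose a patient improved by 6.7 points at once, kept that gain, and averaged evenly over the recall period, with all items treated as 28-day items. All of these are assumptions. He would then report 6.7 × 0.50 = 3.4 points on day 14 and 6.7 × 0.75 = 5.0 on day 21. With visits spread evenly, the mean shortfall would be 6.7 × 0.129 = 0.9 points.

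**The case against.** The strongest reply is that this matters little. Month 1 is a descriptive secondary time point, no decision in the plan depends on it, and a single-arm study has no between-arm contrast to distort. Any understatement of IPSS benefit is in the cautious direction. All of this stands for the IPSS and limits the point to a refinement. The last part does not carry over to the IIEF, where dilution could hide harm.

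A reader might go on to infer three stronger things that the documents do not support.

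- **That the primary analysis is generally biased.** A month-1 score reaches the 12-month analysis only if months 6 and 12 are both missing, and it carries pre-treatment recall only if the visit was early. Section 5.3 provides contact by telephone, email or mail for patients who do not return. Section 6 encourages withdrawn patients to complete the 12-month evaluations. Section 9.5.7 plans multiple-imputation sensitivity analyses if data are judged missing at random. The documents give no basis for putting a probability on this chain.
- **That early scores show half the true benefit.** That needs a visit on the first permitted day, a full and constant effect from day 0, and even averaging over recall. Section 1 itself reports self-limited dysuria and urinary frequency after PAE, which could move an early score on their own.
- **That the quality-of-life item is mixed as well.** It asks about the present condition and is summarised separately from the IPSS total, so it is not affected.

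**Conclusion.** The mismatch is real and minor. The window permits month-1 IPSS and IIEF from day 14. For the 4-week items, 50% of the recall period then lies before PAE, falling to 25% on day 21 and to zero from day 28. The mean is about 13% if visits are spread evenly, which is an assumption about attendance. Under a calendar-month reading the maximum is 39% to 43%.

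These figures are shares of recall time. The resulting bias in score points depends on how patients recall and how quickly symptoms change, and cannot be computed from the documents. The likely direction is toward zero: understated IPSS benefit and possibly a masked early IIEF decline. The planned month-1 changes in IPSS total and IIEF subscales are affected. The primary 12-month comparison is affected only through the LOCF route above.

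**What to change.** In Section 5, Section 5.3 and Appendix A, set the month-1 IPSS and IIEF window to 4 to 6 weeks after PAE (-0/+2 weeks). If the visit itself takes place before day 28, collect the two questionnaires on or after day 28 by telephone, email or mail. Section 5.3 already provides that route for patients who do not return, and its wording would need to cover early attenders too.

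This removes the overlap for every 4-week item. For nocturia, 2 to 3 days can remain at day 28 if a month is read as 30 or 31 days.

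The cost is a change of wording in three places and less scheduling flexibility at one visit. Early attenders need a second contact, and their questionnaires will be dated apart from the ultrasound and uroflowmetry.

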Appendix B: Study Flow Chart

* Cystoscopy and/or anoscopy will be performed for signs or symptoms of bowel or bladder injury, including hematuria, blood per rectum, or greater than expected pelvic pain at any time during the study protocol.

Appendix C: Technical Protocol for Prostate Artery Embolization

- Administer prophylactic IV antibiotics, based on institution standard of care. Choice of antibiotic and sedation will be at the discretion of the interventional radiologist.
- Prior to embolization, insert a Foley catheter into patient's bladder and fill it with a mixture of 50% contrast agent and 50% saline. This will provide a visual landmark during angiography.
- Local anesthesia should be administered for a transfemoral approach on the side with the best arterial pulse.
- Conduct pelvic angiography with a 5Fr catheter to evaluate aortoiliac vessels and prostate arteries during the arterial and late phases.
- Observe closely for vascular conditions and blood flow that might preclude catheter placement or embolic injection, including severe atheromatous disease, arteriovenous shunt, or presence of feeding arteries that are too small to accept the microspheres. If these conditions are present and a viable feeding artery without these problems cannot be identified, embolization will be conducted on the contralateral side of the prostate. If these conditions are present on both sides of the prostate, no embolization will be performed.
- If appropriate, anastomoses to non-targeted vessels and/or endangering collateral vessel pathways will be closed off with a larger size of embolic particles or embolic coils chosen to be appropriate to the size of the anastomosis or collateral vessel. If anastomoses or endangering collateral vessels cannot be closed off, the embolization will be performed only on the contralateral side of the prostate, if it is not affected by the condition. If anastomosis or endangering collateral vessels affects both sides of the prostate, no embolization will be performed.
- If vasospasm occurs, follow institution standard of care, which could include withdrawing the catheter slightly and waiting, or delivering a small amount of nitroglycerin. If the vasospasm cannot be resolved, conduct the embolization only on the contralateral side of the prostate.
- Ensure that the tip of the micro catheter is at or inside the ostium of the prostate arteries with additional angiography.
- Procedural endpoint is stasis of the terminal branches of the arteries feeding the prostate, while maintaining patency of the main artery branches.
 - Histopathology studies have demonstrated that intraprostatic vessels typically have diameters of approximately 300 μm , so embolic particles of 300–500 μm should be used unless an anatomic anomaly is identified.
- Embolize each of the prostate arteries to stasis without reflux of the mixture to undesired arteries. Stasis is defined as persistence of contrast in the target artery for 5 heartbeats.
- Perform follow up angiography after each vessel is embolized to evaluate prostate devascularization and to identify any remaining collateral blood supply to the prostate. All feeding vessels should be embolized.
- When all apparent vessels feeding one side of the prostate are embolized, embolize the other side using the same technique.
- Once the embolization procedure is complete, follow institution's standard of care for catheter and introducer removal and closure of femoral puncture.
- It is suggested to leave the Foley catheter in place for at least 6 hours after procedure. Catheter removal time is at the discretion of the interventional radiologist. After catheter removal PVR will be checked after spontaneous voiding and patients discharged for PVR<250. Otherwise Urology will be contacted for further management.
- It is suggested that patients be discharged with non-opioid analgesic, NSAID, omeprazole and antibiotics for 7 days.

Potential Risks Associated with PAE:

Adverse events that might occur in this study include, but are not limited to:

- For cystoscopy and PAE: Burning sensation in the urethra, urinary infection, hematuria, pain
- General embolization risks: fever, hypotension, hypertension, arterial thrombosis and occlusion, pseudoaneurysm, risks of conscious sedation, amputation, radiodermatitis and death.
- For PAE: Hematospermia, hemorrhage, injury to the bladder (including the bladder neck, ureteral orifice or trigone), impact on future fertility, vasospasm, rectorrhagia, inguinal hematoma, bladder/bladder neck ischemia and necrosis leading to bladder resection, balanitis, erectile dysfunction, rectal ischemia, rectal injury, allergic reaction to Embosphere Microspheres or contrast agent, radiation exposure, vascular perforation, need for subsequent surgery to repair non-target ischemia, and sensory abnormality

The risk of radiation dermatitis will be mitigated by following the standard principles of radiation dose reduction employed in our fluoroscopy laboratory protocols and Interventional Radiology society standards. This includes, but is not limited to, following ALARA principles, monitoring and limiting fluoroscopy time and dose, reducing frame rates when possible, utilizing last-image hold, optimal collimation, reducing magnification, and optimizing imaging geometry. Radiation entry site will be varied as possible to reduce skin entrance doses.

See Embosphere Microsphere IFU for complete product information.

Warnings on the IFU include:

- Embosphere Microspheres do not form aggregates, and as a result, penetrate deeper into the vasculature compared to similar size PVA particles.
- Some Embosphere Microspheres may be slightly outside of the labeled range so the physician should carefully select the size of Embosphere Microspheres according to the size of the target vessels at the desired level of occlusion in the vasculature after consideration of the arteriovenous angiographic appearance.
- Serious radiation induced skin injury may occur to the patient due to long periods of fluoroscopic exposure, large patient diameter, angled x-ray projections, and multiple image runs.
- Careful consideration should be given whenever use is contemplated of embolic agents that are smaller in diameter than the resolution capability of your imaging equipment. The presence of arteriovenous anastomoses, branch vessels leading away from the target area or emergent vessels not evident prior to embolization can lead to mistargeted embolization and severe complications.

